5.5. Study Drug Accountability

The investigator is responsible for ensuring adequate accountability of all used and unused study drug. This includes acknowledgment of receipt of each shipment of study drug (quantity and condition). All unused study drug dispensed to subjects must be returned to the investigator site.

Study drug accountability forms will be provided to each study site to record the following:

- The date received and quantity of study drug received

- The date, subject number, and the study drug kit number dispensed
- The date, quantity of unused study drug returned, along with the initials of the person recording the information

5.5.1. Study Drug Return or Disposal

Gilead recommends that used and unused study drug supplies be destroyed at the site. If the investigator site has an appropriate SOP for drug destruction, as determined by Gilead, the site may destroy used (empty or partially empty) and unused study drug supplies in accordance with that site's approved SOP. A copy of the site's approved SOP must be obtained for electronic trial master file. If study drug is destroyed at the site, the investigator must maintain accurate records for all study drugs destroyed. Records must show the identification and quantity of each unit destroyed, the method of destruction, and the person who disposed of the study drug. Upon study completion, copies of the study drug accountability records must be filed at the site. Another copy must be returned to the sponsor.

If the site does not have an appropriate SOP for drug destruction, used and unused study drug supplies must be sent to the designated disposal facility for destruction. The study monitor will provide instructions for return.

The study monitor will review study drug supplies and associated records at periodic intervals.

For both disposal options listed above, the study monitor must first perform drug accountability.

6. STUDY PROCEDURES

Written informed consent must be obtained prior to the conduction of any study procedure. It is the responsibility of the investigator to ensure that each subject meets all eligibility criteria prior to randomization.

The study procedures to be conducted for each subject enrolled in the study are presented in tabular form in [Appendix 3](#).

Unscheduled visits should be performed, as needed, at the discretion of the investigator. The assessments performed during an unscheduled visit are also at the discretion of the investigator.

The investigator must document any deviation from the protocol procedures and notify the study sponsor.

6.1. Subject Enrollment and Treatment Assignment

Entry into screening does not guarantee enrollment into the study. In order to manage the total study enrollment, Gilead, at its sole discretion, may suspend screening and/or enrollment at any site or study wide at any time.

6.2. Baseline Photography

Baseline, pretreatment photographs must be obtained from an identified cutaneous lesion or area of active disease and provided to the sponsor in a deidentified manner.

The confidentiality of all subjects will be maintained, and photographs of the subjects will not be published nor made public without ensuring complete deidentification of the subject (eg, blocking portions of his/her face or body).

6.3. On-Study Photography

Photography of areas of skin involvement must be performed at the time points indicated in the Study Procedures Table ([Appendix 3](#)). A separate manual will be provided detailing methods of photography.

6.4. Skin Biopsies

Skin biopsies will be performed at the time points indicated in the Study Procedures Table ([Appendix 3](#)). A separate manual will be provided detailing instructions for the collection of skin biopsy samples.

Each biopsy should be performed at the end of the respective visit after all other study procedures have been completed, as much as possible.

6.5. Efficacy Assessments

Efficacy assessments will be performed at the time points indicated in the Study Procedures Table ([Appendix 3](#)).

6.5.1. Cutaneous Lupus Erythematosus Disease Area and Severity Index (CLASI)

The CLASI is a standardized, validated measure of cutaneous lupus disease activity and damage, widely used in clinical trials. CLASI-A scores range from 0 to 70, with higher scores indicating more severe disease activity.

6.5.2. Systemic Lupus Erythematosus Disease Activity Index 2000 (SLEDAI-2K)

The SLEDAI-2K is a validated measure of global disease activity, commonly used in SLE clinical trials. The SLEDAI-2K assesses the presence/absence of disease activity across 9 organ systems, with total scores that range from 0 to 105; higher scores indicating more severe disease activity. The SLEDAI-2K is only to be administered to subjects with concurrent SLE.

6.5.3. Physician's Global Assessments of CLE Disease Activity

The PGA of CLE disease activity will be recorded on a 0 to 100 mm VAS, with 0 indicating "no CLE disease activity" and 100 indicating "maximum CLE disease activity". The evaluating physician and the subject should complete the global assessments independently of each other.

6.5.4. Subject's Global Assessments of CLE Disease Activity

The SGA of CLE disease activity will be recorded on a 0 to 100 mm VAS, with 0 indicating "I have no CLE" and 100 indicating "I have the worst CLE."

6.6. Assessments for Early Discontinuation from Study

If a subject discontinues study dosing (eg, as a result of an AE), every attempt should be made to keep the subject in the study and continue to perform the required study-related follow up and procedures (see Section 3.5.2). If this is not possible or acceptable to the subject or investigator, the subject may be withdrawn from the study.

7. ADVERSE EVENTS AND TOXICITY MANAGEMENT

7.1. Definitions of Adverse Events and Serious Adverse Events

7.1.1. Adverse Events

An AE is any untoward medical occurrence in a clinical study where the subject is administered a study drug, which does not necessarily have a causal relationship with the treatment. An AE can therefore be any unfavorable and/or unintended sign, symptom, or disease temporally associated with the use of a study drug, whether or not the AE is considered related to the study drug. Adverse events may also include pretreatment or posttreatment complications that occur as a result of protocol-specified procedures or special situations (Section 7.1.3).

An AE does not include the following:

- Medical or surgical procedures such as surgery, endoscopy, tooth extraction, and transfusion. The condition that led to the procedure may be an AE and must be reported
- Preexisting diseases, conditions, or laboratory abnormalities present or detected before the screening visit that do not worsen
- Situations where an untoward medical occurrence has not occurred (eg, hospitalization for elective surgery, social and/or convenience admissions)
- Overdose without clinical sequelae (Section 7.1.3)
- Any medical condition or clinically significant laboratory abnormality with an onset date before the ICF is signed and not related to a protocol-associated procedure is not an AE but rather considered to be preexisting and should be documented in the medical history eCRF.

Preexisting events that increase in severity or change in nature after study drug initiation or during or as a consequence of participation in the clinical study will also be considered AEs.

7.1.2. Serious Adverse Events

An SAE is defined as an event that, at any dose, results in the following:

- Death
- A life-threatening situation (Note: The term “life-threatening” in the definition of “serious” refers to an event in which the subject was at risk of death at the time of the event; it does not refer to an event that hypothetically might have caused death if it were more severe.)
- Inpatient hospitalization or prolongation of existing hospitalization

- Persistent or significant disability/incapacity
- A congenital anomaly/birth defect
- A medically important event or reaction: Such events may not be immediately life-threatening or result in death or hospitalization but may jeopardize the subject or may require intervention to prevent one of the other outcomes constituting SAEs. Medical and scientific judgment must be exercised to determine whether such an event is reportable under expedited reporting rules. Examples of medically important events include intensive treatment in an emergency room or at home for allergic bronchospasm; blood dyscrasias or convulsions that do not result in hospitalization; and development of drug dependency or drug abuse.

7.1.2.1. Protocol-Specific Adverse Event Definitions

Protocol-specific AE reporting exemptions:

- Laboratory abnormalities that are not deemed clinically significant and are not associated with symptoms are not considered AEs
- ECG changes that are not deemed clinically significant and are not associated with symptoms are not considered AEs

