3.5.2. Study Drug Discontinuation Criteria

The sponsor medical monitor should be consulted prior to study drug discontinuation, when medically feasible.

Study drug should be permanently discontinued in the following circumstances:

- Any opportunistic infection
- Any Grade 2 or higher cardiovascular or hematologic event (or Grade 3 lymphopenia or anemia as described below under "Laboratory Criteria")
- Any serious infection that requires antimicrobial therapy or hospitalization, or any infection that meets SAE reporting criteria
- Unacceptable toxicity, or toxicity that, in the judgment of the investigator, compromises the subject's ability to continue study-specific procedures or is considered to not be in the subject's best interest
- Subject request to discontinue for any reason
- Subject noncompliance, per investigator judgment
- Investigator discretion
- Female subject becomes pregnant during the study
 - NOTE: If the female partner of a male subject becomes pregnant during the study, the investigator, in consultation with the Gilead medical monitor, will determine whether the subject should continue in the study on a case-by-case basis.
- Discontinuation of the study at the request of the study sponsor, a regulatory agency or an institutional review board (IRB)/independent ethics committee (IEC)

- Subject use of prohibited concurrent systemic therapy
- An absolute QTcF > 500 msec or a change from the baseline QTcF value > 60 msec
- Laboratory Criteria: After becoming aware of any of the abnormal laboratory values below, study drug should be paused, and an unscheduled visit (ie, sequential visit) should occur to retest within 3 to 7 days (except creatinine, which should be retested 7 to 14 days apart). Retest may be obtained sooner if medically indicated, per investigator judgment.
- If the laboratory abnormality is confirmed by the retest, then study drug should be permanently discontinued.
 - Hemoglobin < 8.0 g/dL (International System of Units [SI]: < 80.0 g/L)
 - ANC < 1500 cells/mm³ (SI: < 1.5 × 10⁹ cells/L)
 - Lymphocyte count < 500 cells/mm³ (SI: < 0.5 × 10⁹ cells/L)
 - Platelet count < 75,000 cells/mm³ (SI: < 75 × 10⁹ cells/L)
 - Any AST and/or ALT ≥ 3 × ULN independent of signs of liver damage
 - Estimated CL_{cr} < 60 mL/min based on the Cockcroft-Gault equation

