7.5. Gilead Reporting Requirements

Depending on relevant local legislation or regulations, including the applicable US FDA Code of Federal Regulations, the EU Clinical Trials Directive (2001/20/EC) and relevant updates, and other country-specific legislation or regulations, Gilead may be required to expedite to worldwide regulatory agencies reports of SAEs which may be in the form of line listings, serious adverse drug reactions, or suspected unexpected serious adverse reactions (SUSARs). In accordance with the EU Clinical Trials Directive (2001/20/EC), Gilead or a specified designee will notify worldwide regulatory agencies and the relevant IEC in concerned Member States of applicable SUSARs as outlined in current regulations.

Assessment of expectedness for SAEs will be determined by Gilead using reference safety information specified in the IB or relevant local label as applicable.

All investigators will receive a safety letter notifying them of relevant SUSAR reports associated with any study drug. The investigator should notify the IRB or IEC of SUSAR reports as soon as is practical, where this is required by local regulatory agencies, and in accordance with the local institutional policy.

7.6. Clinical Laboratory Abnormalities and Other Abnormal Assessments as Adverse Events or Serious Adverse Events

Laboratory abnormalities without clinical significance are not to be recorded as AEs or SAEs. However, laboratory abnormalities (eg, clinical chemistry, hematology, urinalysis) that require medical or surgical intervention or lead to study drug interruption, modification, or discontinuation must be recorded as an AE, as well as an SAE, if applicable. In addition, laboratory or other abnormal assessments (eg, ECG, X-rays, vital signs) that are associated with signs and/or symptoms must be recorded as an AE or SAE if they meet the definition of an AE or SAE as described in Sections 7.1.1 and 7.1.2. If the laboratory abnormality is part of a syndrome, record the syndrome or diagnosis (eg, anemia), not the laboratory result (ie, decreased hemoglobin).

Severity should be recorded and graded according to the CTCAE. For AEs associated with laboratory abnormalities, the event should be graded on the basis of the clinical severity in the context of the underlying conditions; this may or may not be in agreement with the grading of the laboratory abnormality.

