#### 7.1.6. Summaries of Adverse Events and Deaths

Treatment-emergent AEs will be summarized based on the Safety Analysis Set.

A brief, high-level summary of the number and percentage of participants who experienced at least 1 TEAE in the categories described below will be provided by treatment group. All deaths observed in the study will also be included in this summary.

The number and percentage of participants who experienced at least 1 TEAE will be provided and summarized by treatment group for the following:

- TEAEs
- TEAEs with Grade 3 or higher
- TEAEs with Grade 2 or higher
- TEAE Related to Study Drug
- TEAE Related to Study Drug with Grade 3 or Higher
- TEAE Related to Study Drug with Grade 2 or Higher
- TE Serious AE
- TE Serious AE Related to Study Drug
- TEAE leading to discontinuation of study drug
- TEAE leading to discontinuation of study
- TE AE leading to death (i.e., outcome of death)

Multiple events will be counted only once per participant in each summary.

In addition, data listings will be provided for all AEs and all SAEs indicating whether the event is treatment emergent, and all deaths.

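### An asymptomatic QTcF change that stops study drug need not be recorded as an AE, so it can be absent from the primary AE count

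*Protocol*

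**What the plan says.** **Stop rule.** Among the circumstances for permanent discontinuation, Protocol 3.5.2 lists "An absolute QTcF > 500 msec or a change from the baseline QTcF value > 60 msec". It attaches no condition about symptoms or clinical significance.

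**AE exemptions.** Protocol 7.1.2.1 has two parallel bullets. One says that "ECG changes that are not deemed clinically significant and are not associated with symptoms are not considered AEs"; the other says that "Laboratory abnormalities that are not deemed clinically significant and are not associated with symptoms are not considered AEs". Neither makes an exception for findings that stop study drug.

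**Recording rule.** Protocol 7.6 opens with "Laboratory abnormalities without clinical significance are not to be recorded as AEs or SAEs". It then turns to laboratory abnormalities "that require medical or surgical intervention or lead to study drug interruption, modification, or discontinuation must be recorded as an AE". ECGs appear only in the following sentence, under which laboratory or "other abnormal assessments (eg, ECG, X-rays, vital signs) that are associated with signs and/or symptoms must be recorded as an AE" or SAE, provided the AE or SAE definition is also met.

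**Endpoints and outputs.** Protocol 8.1.2 has two primary endpoints: the count of subjects with AEs and the count with laboratory abnormalities. SAP 7.1.6 tabulates, among other rows, "TEAE leading to discontinuation of study drug". SAP 4.1 tabulates reasons for stopping study drug by treatment group. SAP 7.5 provides ECG results as by-participant listings only.

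**The concern.** The protocol treats a QTcF change of this size as reason enough to end dosing, yet its recording rules let the same finding go without an AE entry. A laboratory value with the same consequence has to be entered. The AE count is a primary endpoint and safety is the primary objective, so the count should not depend on which kind of test led to the stop.

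QTcF is also a finding of some interest here. Protocol 1.2.2 reports mild QT prolongation at the high dose in the monkey cardiovascular study, although it rates the clinical risk as low. The second primary endpoint offers no backup, because it covers laboratory abnormalities and not ECGs.

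**Working it through.** The plan gives no figure to reproduce; the check is a comparison of texts, with simple arithmetic for scale.

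**Step 1. Follow one finding through each rule.** Take a finding that meets a 3.5.2 criterion, causes no symptoms and is judged not clinically significant.

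| Rule | Laboratory value | QTcF change |
|---|---|---|
| 3.5.2 | Pause and retest; discontinue if confirmed | Discontinue permanently |
| 7.1.2.1 | Not an AE | Not an AE |
| 7.6, action-taken clause | Must be recorded as an AE | Not named |
| 7.6, signs-and-symptoms clause | Not triggered | Not triggered |
| Second primary endpoint (8.1.2) | Covered if the value is a treatment-emergent graded abnormality | Not covered |

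For the laboratory value, 7.6 requires a record. For the QTcF change, no section does. Nor does any section say that meeting a 3.5.2 criterion makes a finding clinically significant.

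**Step 2. Does the SAP recover the event?** The second part of the TEAE definition in SAP 7.1.5.1 adds AEs that lead to premature discontinuation of study drug. It works only on events already entered as AEs, and the discontinuation row in SAP 7.1.6 has the same dependence. The subject is therefore absent from that row, and also from the overall TEAE row unless another AE was recorded.

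**Step 3. Where does the event still appear?** In the disposition table and listing of reasons for stopping study drug (SAP 4.1), and in the ECG listing (SAP 7.5). Protocol 8.5.4.1 had planned a summary of ECG data by treatment group. SAP 7.7 explains that only limited safety summaries are given because so few participants were enrolled.

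**Step 4. Size of one omission.** The inputs are 8 active and 4 placebo subjects planned (Protocol 8.9) and 3 enrolled (SAP 1). If the subject has no other AE, the proportion with any AE falls by 1/n:

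- planned active arm: 1/8 = 12.5 points
- planned placebo arm: 1/4 = 25 points
- all enrolled: 1/3 = 33.3 points

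The documents do not give the arm split of the 3. The shift within an arm would be 1/2 = 50 points for an arm of 2, or 100 points for an arm of 1. If the subject has another AE, the overall AE count does not change and only the discontinuation row is short by one.

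**Step 5. How often?** The documents give no rate of QTcF triggers. Taking 1% to 5% per subject purely as an assumption, the chance of at least one trigger is 1 − (1 − p)^n:

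- n = 8: 1 − 0.99^8 = 7.7%, and 1 − 0.95^8 = 33.7%
- n = 3: 1 − 0.99^3 = 3.0%, and 1 − 0.95^3 = 14.3%

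These are chances of any trigger. An unrecorded stop also needs the change to be asymptomatic and judged not clinically significant, so at the same assumed rates its chance can only be equal or lower.

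**The case against.** The strongest reply is that the gap needs an unlikely chain. QTcF must cross the limit without symptoms, and the investigator must end dosing yet call the change not clinically significant. If the change is called significant, 7.1.2.1 no longer exempts it and the general definition in 7.1.1 would make it an AE. The sponsor medical monitor should be consulted before discontinuation where feasible, and sponsor staff are unblinded. ECGs are scheduled at screening, Week 2, Week 4, early termination and follow-up. Week 2 is thus the only routine on-treatment ECG before the visit that ends treatment. Protocol 1.2.3.1 reports no clinically relevant ECG abnormalities in healthy subjects. All of this stands. It makes the event rare, but does not close the gap in the text.

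Four stronger readings are tempting and are not supported:

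- **That the event would vanish from every table.** SAP 4.1 tabulates reasons for stopping study drug. What is lost is the AE-based count and the TEAE discontinuation row.
- **That 7.1.2.1 and 7.6 leave sites with no answer on laboratory values.** The 7.1.2.1 laboratory bullet does lack the exception. But 7.6 states the general rule and then expressly overrides it for findings that lead to action on study drug, which is a specific instruction. Graded laboratory abnormalities are also a separate primary endpoint, tabulated from the values (SAP 7.2.2.1 and 7.2.2.2) whether or not an AE is entered.
- **That the first-in-human tables show the problem at work.** Table 1-2 has 4 subjects with Grade 3 laboratory abnormalities and Table 1-1 has no TEAE of Grade 3 or higher. That is another study, whose recording rules are not shown, and it concerns laboratory values. Protocol 7.2.2 also allows an AE grade to differ from the laboratory grade.
- **That the stop is strictly mandatory.** The verb in 3.5.2 is *should*.

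A final objection is that amending recording rules cannot change what was collected in a discontinued study. That is right, and it is why the fix includes a step for the report.

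**Conclusion.** The concern holds for ECG findings. Followed as written, the protocol permits a QTcF-triggered stop with no AE record, and so a subject missing from the primary AE count and from the TEAE discontinuation row. This depends on the change being both asymptomatic and judged not clinically significant. The shift of 12.5, 25 or 33.3 points further requires that the subject has no other AE. The trigger rates used for scale are assumptions, and nothing in the documents shows that such an event occurred among the 3 participants.

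The laboratory mismatch is a lesser drafting point of limited effect. Overall this is an inconsistency worth correcting, because it touches a primary endpoint and costs little to remove; it does not show that any result is wrong.

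**What to change.** **Protocol.** Reconcile 3.5.2, 7.1.2.1 and 7.6 on AE recording. In 7.6, extend the clause on abnormalities that "lead to study drug interruption, modification, or discontinuation must be recorded as an AE" so that it covers ECG and vital-sign abnormalities as well as laboratory ones. In 7.1.2.1, add to both bullets: *except where Section 7.6 requires recording*.

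**Abbreviated CSR.** Check each participant against the laboratory and QTcF criteria in 3.5.2. Report how many met one with no AE recorded, even if the number is zero. Put this on a separate line beside the TEAE table. It cannot go inside a TEAE row, because a participant without an AE does not meet the SAP's TEAE definition, and SAP 7.1.6 has no interruption row.

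**Cost.** Two wording changes in the protocol and one reported line, checked for 3 participants. The downside is that a few more asymptomatic AEs may be recorded. No threshold or clinical rule changes.

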7.1.3. Study Drugs and Gilead Concomitant Therapy Special Situations Reports

Special situation reports (SSRs) include all reports of medication error, abuse, misuse, overdose, occupational exposure, drug interactions, exposure via breastfeeding, unexpected benefit, transmission of infectious agents via the product, counterfeit or falsified medicine, and pregnancy regardless of an associated AE.

Medication error is any unintentional error in the prescribing, dispensing, preparation for administration or administration of a study drug while the medication is in the control of a health care professional, patient, or consumer. Medication errors may be classified as a medication error without an AE, which includes situations of missed dose, medication error with an AE, intercepted medication error, or potential medication error.

Abuse is defined as persistent or sporadic intentional excessive use of a study drug by a subject.

Misuse is defined as any intentional and inappropriate use of a study drug that is not in accordance with the protocol instructions or the local prescribing information.

An overdose is defined as an accidental or intentional administration of a quantity of a study drug given per administration or cumulatively which is above the maximum recommended dose as per protocol or in the product labelling (as it applies to the daily dose of the subject in question). In cases of a discrepancy in drug accountability, overdose will be established only when it is clear that the subject has taken the excess dose(s). Overdose cannot be established when the subject cannot account for the discrepancy, except in cases in which the investigator has reason to suspect that the subject has taken the additional dose(s).

Occupational exposure is defined as exposure to a study drug as a result of one's professional or nonprofessional occupation.

Drug interaction is defined as any drug/drug, drug/food, or drug/device interaction.

Unexpected benefit is defined as an unintended therapeutic effect where the results are judged to be desirable and beneficial.

Transmission of infectious agents is defined as any suspected transmission of an infected agent through a Gilead study drug.

Counterfeit or falsified medicine: Any study drug with a false representation of (a) its identity, (b) its source, or (c) its history.

